7. PROTOCOL DEVIATIONS

Investigators are not allowed to deviate from the protocol without prior authorization by the sponsor except under emergency situations when necessary to preserve the rights, safety, and well-being of human subjects.

All deviations from the protocol should be reported on a protocol deviation eCRF, and a reason for the deviation should be noted. Additionally, the investigator (or designee) is also required to report protocol deviations to the IRB if the protocol deviations are required to be reported per the IRB reporting requirements. Deviations that impact the rights, welfare, or safety of patients shall be reported to the sponsor and IRB as soon as possible.

If Acera Surgical, Inc. becomes aware that an investigator is not complying with any part of the protocol, including signed agreements, or any conditions of approval imposed by the reviewing IRB/EC, Acera will promptly secure compliance and may suspend the investigator's participation (including enrollment at the site).

8. RISKS AND BENEFITS

For a complete list of risks and benefits that may occur with the use of approved synthetic hybrid-scale fiber matrix, Standard of Care, and living cellular skin substitute, refer to the Instructions for Use.

9. STATISTICAL CONSIDERATIONS

9.1 Hypotheses to be Tested

9.1.1 Primary Endpoints:

9.1.1.1 DFU Arm

The null hypothesis (H_0) for the primary endpoint in the DFU arm is that the difference in proportion of patients achieving 100% re-epithelialization by week 12 between the synthetic hybrid-scale fiber matrix group (π_1) and the control group (π_2) is less than or equal to the noninferiority margin of -0.10 based on a one-sided Farrington & Manning test. The alternative hypothesis (H_1) is that the difference is greater than the noninferiority margin of -0.10. These can be seen in the equations below:

$$H_0: \pi_1 - \pi_2 \leq -0.10$$

$$H_1: \pi_1 - \pi_2 > -0.10$$

9.1.1.2 VLU Arm

The null hypothesis (H_0) for the primary endpoint in the VLU arm is that the difference in proportion of patients achieving 100% re-epithelialization by week 16 between the synthetic hybrid-scale fiber matrix group (π_1) and the control group (π_2) is less than or equal to the noninferiority margin of -0.10 based on a one-sided Farrington & Manning test. The alternative hypothesis (H_1) is that the difference is greater than the noninferiority margin of -0.10. These can be seen in the equations below:

$$H_0: \pi_1 - \pi_2 \leq -0.10$$

$$H_1: \pi_1 - \pi_2 > -0.10$$

9.2 Analysis Populations

Intention to Treat Population (ITT)

The ITT population will consist of all enrolled patients. Patients are considered enrolled after meeting the criteria specified in Section 5.6. Patients in the ITT population will be evaluated based on the randomized treatment group.

Modified Intention to Treat Population (mITT)

The mITT population will consist of ITT patients who have at least one product application. This will serve as the primary analysis population for study efficacy. Patients in the mITT population will be evaluated based on the randomized treatment group.

Per Protocol (PP)

The PP will include all ITT patients who additionally meet all study eligibility criteria, have available study data for the primary study endpoint and do not have a major protocol violation that affects primary effectiveness. Patients in the PP population will be evaluated based upon the treatment that they receive.

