3. STUDY DESIGN

Conditions : Diabetic Foot Ulcers (DFU) and Venous Leg Ulcers (VLU)

Aim: Assessment of complete wound re-epithelialization by comparing synthetic hybrid-scale fiber matrix with SOC in treating DFUs and with living cellular skin substitute in treating VLUs

Study Type: Interventional

Study Design: Prospective, randomized, single-blinded, comparison, non-inferiority study

Control Group: SOC for DFU patients and living cellular skin substitute for VLU patients

Test Group: Synthetic hybrid-scale fiber matrix for patients with DFUs and VLUs

Number of Sites: Up to 10

Number of Subjects:

- **Diabetic Foot Ulcers:** The initial planned enrollment is 110 patients, with no more than 27 DFU patients enrolled at each site. An interim analysis will be performed after 56 patients complete the primary endpoint. Based on the interim analysis result, the enrollment size may be increased to a maximum of 166 patients with a maximum of 41 DFU patients at each site.
- **Venous Leg Ulcers:** The initial planned enrollment is 60 patients, with no more than 15 VLU patients enrolled at each site. An interim analysis will be performed after 30 patients complete the primary endpoint. Based on the interim analysis result, the enrollment size may be increased to a maximum of 90 patients with a maximum of 22 VLU patients at each site.

Primary Outcome Measure:

- **Diabetic Foot Ulcers:**
100% re-epithelialization of wound as assessed by the blinded evaluator via the eKARE inSight platform within 12 weeks after the initial application of the study product plus confirmation of no drainage or need for additional dressing 2 weeks after 100% re-epithelialization
- **Venous Leg Ulcers:**
100% re-epithelialization of wound as assessed by the blinded evaluator via the eKARE inSight platform within 16 weeks after the initial application of the study product plus confirmation of no drainage or need for additional dressing 2 weeks after 100% re-epithelialization

Secondary Outcome Measures:

- Decrease in Wound Area from Initial Application
Wound area measurements will be made via the eKare inSight platform every week for 12 weeks for DFU patients and 16 weeks for VLU patients, or until 100% re-epithelialization, whichever occurs first.
- Time to 100% re-epithelialization
The number of weeks from initial application of study product until 100% re-epithelialization is first identified.

- Number of Product Applications

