5.13 Two Week Visit to Confirm Wound Closure

An in-person visit with the patient to confirm 100% re-epithelialization will be completed two weeks (± 3 days) following the visit when 100% re-epithelialization was first identified and documented. A clinic visit is NOT required if there is not complete wound re-epithelialization of any wound at 12 weeks or earlier for DFU patients (or 16 weeks or earlier for VLU patients). For patients with more than one wound, an in-person follow-up visit will be completed two weeks following 100% re-epithelialization of each wound.

Research personnel will complete the following:

- Measurement and imaging of wound area via the eKare inSight platform according to the eKare inSight instructions.
- Wound drainage since the previous visit
- Additional dressing changes since the previous visit
- Adverse events
- Review wound imaging to confirm the wound remains closed

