5.15 Study Exit

5.15.1 Study Participation Exit Points

A patient's participation in the study will end after any of the following:

- DFU patients without 100% re-epithelialization of at least one study wound: at 12 weeks
- VLU patients without 100% re-epithelialization of at least one study wound: at 16 weeks

- Completion of six-month telephone call (for patients with 100% re-epithelialization of at least one study wound)
- Patient withdrawal
- The Investigator may withdraw the patient if he/she determines it is in the patient's best interest
- Patient lost to follow-up
- Amputation of all or part of the study limb
- Closure of study
- Patient death

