5.15.2 Patient Withdrawal

A patient (or patient's LAR) may choose to withdraw from the study at any time without penalty or loss of benefits. The patient should notify the investigator (or designee) of his/her desire to withdraw, and the investigator (or designee) should ask for and document the reason for withdrawal. The investigator may also choose to withdraw a patient from the study at any time if he/she considers it to be in the patient's best interest. The reason for withdrawal should be recorded. Any data collected on the patient up to the point of withdrawal may be used in the study.

If complete wound closure has not been confirmed at the time of withdrawal from the study, then the investigator should attempt to determine the status of the wound at the time of the patient's withdrawal to the best of the patient's ability (i.e., healed, not healed, seeking additional treatment, not seeking additional treatment) and to complete as many of the patient-reported outcomes questionnaires as the patient is able and willing to complete.

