9.6 Strategies to Address Missing Data

Patients who are missing complete wound closure will be considered as “missing data patients”. Missing complete wound closure status will be imputed using a logistic regression multiple imputation approach for dichotomous outcome data. In this approach, missing healing status will be imputed from logistic regression models with independent variables of age, gender, and other variables to be specified in the formal statistical analysis plan. This will be performed 50 times in each arm in order to generate 50 “complete” datasets. For the DFU arm, the one-sided Farrington & Manning test for assessing treatment difference will be carried out on each of the 50 complete datasets, with the results being combined across the 50 complete datasets using standard multiple imputation theory to obtain one overall p-value comparing the two treatments on the primary endpoint after accounting for missing data. Similarly for the VLU arm, the one sided Fisher’s Exact test for assessing treatment difference will be carried out on each of the 50 complete datasets, with the results being combined across the 50 complete datasets using standard multiple imputation theory to obtain one overall p-value comparing the two treatments on the primary endpoint after accounting for missing data.

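### The plan has no rule for a closure whose two-week confirmation visit is missed; data go missing at this step only among closers, which can understate closure and, if miss rates differ between groups, bias the comparison

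*Combined protocol and SAP*

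**What the plan says.** - **Outcome definition.** Sections 1 and 3 require closure within 12 or 16 weeks "plus confirmation of no drainage or need for additional dressing 2 weeks after 100% re-epithelialization".
- **Who has the second visit.** Section 5.13 says: "A clinic visit is NOT required if there is not complete wound re-epithelialization of any wound at 12 weeks or earlier for DFU patients", and sets the same rule for VLU at 16 weeks. The schedules in 5.1 and 5.2 agree. Under 5.15.1, patients with no closed wound leave the study at the end of treatment ("DFU patients without 100% re-epithelialization of at least one study wound: at 12 weeks").
- **Hypotheses and analysis.** Section 9.1.1.1 tests the "difference in proportion of patients achieving 100% re-epithelialization by week 12", and 9.1.1.2 does the same at Week 16. Section 9.5.4 also words the endpoint as closure at Week 12 or 16 and mentions the confirmatory visit in a separate sentence.
- **Populations.** Of mITT, section 9.2 says: "This will serve as the primary analysis population for study efficacy". The per-protocol set takes only patients who "have available study data for the primary study endpoint"; what makes data available is not defined.
- **Missing data.** Section 9.6 says: "Missing complete wound closure status will be imputed using a logistic regression multiple imputation approach for dichotomous outcome data". The named predictors are age and gender, with others deferred to a formal SAP. The 50 imputations are run by arm, which in this document means DFU or VLU, not treatment group.

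**The concern.** A patient seen at Week 12 or 16 with an open wound has complete primary data. A patient whose wound closed has complete data, under the sections 1 and 3 definition, only after one more visit. At this step missing data can therefore arise only among patients already read as closed, so missingness depends on the outcome.

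If that definition governs 9.2 and 9.6, the per-protocol data condition removes closers at this step and never removes a failure. In mITT, the imputation sets aside the closure already read and draws the whole endpoint again from a model that need not use it. If 9.1 and 9.5.4 govern, the same patient is simply a success. The plan thus allows incompatible scorings of the same patient, and the choice could be made after the data are seen. What is at stake is the closure rate in each group and the difference tested against the −10-point margin.

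**Working it through.** **Inputs from the documents (9.1.1, 9.3).** Closure 75% vs 60% (DFU) and 75% vs 50% (VLU); margin −0.10; one-sided alpha 0.05; power 0.8; 44 and 24 per group; 20% loss; 110 DFU patients, so 55 per group. **Assumption.** The share m of closers who miss the two-week visit is not given; I use 5% to 20%.

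**1. The plan's own figure.** Farrington–Manning: n = [z₀.₉₅√V₀ + z₀.₈₀√V₁]² / (Δ + 0.10)², with V₀ at the restricted estimates (61.6% and 71.6% for DFU).
- DFU: (1.645·√0.4402 + 0.842·√0.4275)² / 0.25² = 43.1, so 44; 88/0.8 = 110.
- VLU: 23.1, so 24; 48/0.8 = 60.

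Both reproduce, and this concern does not affect them.

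**2. Equal miss rates, patients dropped.** If the missed wounds stayed closed, the observed rate is p(1−m)/(1−pm). At m = 10%: 0.675/0.925 = 73.0% and 0.54/0.94 = 57.4%. Imputing within group without closure status has the same expected rate.

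| m (both groups) | Matrix (true 75%) | Control (true 60%) | Difference (true 15.0) |
|---|---|---|---|
| 5% | 74.0% | 58.8% | 15.3 |
| 10% | 73.0% | 57.4% | 15.5 |
| 20% | 70.6% | 54.5% | 16.0 |

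For VLU at m = 10% the difference is 25.6 against 25.0. At the DFU null (50% vs 60%) with m = 20%, it is 44.4% − 54.5% = −10.1. If treatment is left out of the imputation model, the planned DFU difference moves by −0.3 to −1.1 points, and the VLU difference by up to −2.1.

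**3. Unequal miss rates (assumed).** Exact enumeration of the test, 55 per group, averaged over the random number dropped:

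| True rates | Missed, matrix / control | Handling | Observed difference | P(non-inferiority) |
|---|---|---|---|---|
| 50 vs 60 | 0 / 0 | – | −10.0 | 5.0% |
| 50 vs 60 | 5% / 15% | dropped | 48.7 − 56.0 = −7.3 | 8.7% |
| 50 vs 60 | 5% / 15% | failure | 47.5 − 51.0 = −3.5 | 15.9% |
| 75 vs 60 | 0 / 0 | – | 15.0 | 0.88 |
| 75 vs 60 | 15% / 5% | dropped | 71.8 − 58.8 = 13.1 (unrounded rates) | 0.79 |
| 75 vs 60 | 15% / 5% | failure | 63.75 − 57.0 = 6.75 | 0.58 |

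Fixing the retained numbers at their expected values gives 8.1% in place of 8.7%. Starting from 44 per group gives 9.4% (4.6% with no misses), and power of 81.7% falling to 71.5%. With equal rates of 10% or 20% and dropping, false non-inferiority at 55 per group stays at 4.9% to 5.0%.

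**4. Is the direction fixed?** No.
- Let q be the share of missed wounds that would have been confirmed. The true rate is p(1−m) + pmq. At m = 10% it equals the observed rate when q is about 73% (p = 75%) or 57% (p = 60%). Below that, dropping overstates closure.
- If a share l of non-closers is lost before Week 12, the observed rate is p(1−m)/[p(1−m) + (1−p)(1−l)]. With m = l = 10% this is exactly 75.0% and 60.0%. With l = 20% it is 77.1% and 62.8%.

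**The case against.** A reader might infer that the plan drops or re-draws known closures, and so always understates closure and biases the difference. The documents do not support that, for these reasons:

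- No section says that a missed two-week visit makes a patient missing. On the wording of 9.1.1 and 9.5.4 such a patient has endpoint data, and nothing is dropped or imputed.
- Under sections 1 and 3 an unconfirmed closure is not yet a success, so calling it a known closure assumes the answer.
- Non-closers must keep attending to Week 12 or 16, while weekly visits stop once all wounds have closed (5.10). Losses among non-closers push the observed rate the other way. The documents give only a 20% overall loss.
- The large effects need unequal miss rates. None are documented, and both groups have the same confirmation visit.
- mITT, not per-protocol, is primary, and 9.6 leaves further predictors open.
- Other data exist. A missed visit does not by itself end participation (5.15.3). The six-month call asks about closure, drainage and dressings (5.14). Under 5.15.2, wound status is sought "If complete wound closure has not been confirmed at the time of withdrawal from the study".

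The first four points stand, and they make the conclusion conditional. The last two weaken the concern without removing it. Section 9.6 carries the gap into mITT, an open list of predictors is not a commitment to use observed closure, and no rule lets the call or the withdrawal status count as confirmation. Unequal missing is also possible: study personnel obtain the assignment (5.8) and apply different products on different DFU schedules (5.10).

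**Conclusion.** The concern holds in conditional form. The asymmetry is in the text, sections 9.2 and 9.6 give no rule for an unconfirmed closure, and the one-step imputation names neither the closure already read nor treatment group.

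If the two-part definition governs and the missed wounds stayed closed, closure is understated by 1.0 to 4.4 points at 75% and by 1.2 to 5.5 points at 60%, for assumed miss rates of 5% to 20%. Reopening among missed wounds, or loss of non-closers, can cancel or reverse this.

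The group difference is materially affected only if the groups differ in miss rate or in how often missed wounds would have been confirmed. With equal rates and dropping, the shift is about 1 point or less. Under an assumed 5%/15% split, false non-inferiority is about 8–9% instead of 5.0% (15.9% if misses are scored as failures). With the split reversed, power is 0.79 instead of 0.88. These figures illustrate sensitivity; they do not predict what will happen in this trial.

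**What to change.** In 9.5.4 and 9.6, define the endpoint in two steps:

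1. No closure read at a completed Week 12 or 16 visit is an observed failure.
2. Closure with a confirmation visit is observed. A late in-person confirmation also counts, with a deviation recorded.
3. For closure without confirmation in mITT, keep the closure and impute only the confirmation component, within treatment group, from closers who were seen.

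In 9.2, state how unconfirmed closures are handled in the per-protocol set. Keeping a patient with an imputed component there is debatable, so the choice should be explicit and made in advance. Say also whether the six-month call or the wound status at withdrawal may serve as confirmation. Add a sensitivity analysis that scores every unconfirmed closure as closed and then as not closed; it needs no assumption about why the visit was missed. Align the endpoint wording in 9.1.1 and 9.5.4 with sections 1 and 3.

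The cost is a few lines of SAP text, one imputation step and one extra analysis, with no added patients or scheduled visits. The main imputation does assume that, among closers within a group, missing the visit is unrelated to reopening; the sensitivity analysis shows how much that matters.

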9.3 Sample Size Calculation

9.3.1 DFU Arm

Sample size calculations were performed using a Farrington & Manning test for non-inferiority of the synthetic hybrid-scale fiber matrix group compared to the control group. Under assumptions of a closure rate of 75% for the synthetic hybrid-scale fiber matrix group, 60% for the control group, and a noninferiority margin of 10%, this results in a sample size of 44 per group (88 total) that provides a power of 0.8 and one-sided alpha of 0.05. After allowing for an assumed 20% lost to follow up, this results in a total sample size of 110 patients.

9.3.2 VLU Arm

Sample size calculations were performed using a Farrington & Manning test for non-inferiority of the synthetic hybrid-scale fiber matrix group compared to the control group. Under assumptions of a closure rate of 75% for the synthetic hybrid-scale fiber matrix group, 50% for the control group, and a noninferiority margin of 10%, this results in a sample size of 24 per group (48 total) that provides a power of 0.8 and one-sided alpha of 0.05. After allowing for an assumed 20% lost to follow up, this results in a total sample size of 60 patients.

9.4 Interim and Final Analyses

An unblinded interim assessment for sample size re-estimation (SSR) will be performed on the primary endpoint in each arm of the study by an independent statistician.

9.4.1 DFU Arm

In the DFU arm, the analysis will be conducted when 50% of the mITT population (56 patients) have been enrolled and completed the primary endpoint evaluation. The analysis described below will be performed on the mITT population.

The purposes of the interim analysis are (1) to calculate the power for non-inferiority, conditioned on the interim-observed difference between treatments with respect to 100% re-epithelialization rates and on the non-inferiority margin of 10%, and (2) determine if the sample size needs to be increased in order to maintain the desired conditional power of 80%.

The conditional power will be calculated under the assumption that the interim observed estimate of the treatment difference is the true treatment difference. It will be calculated using the following formula as discussed in Lan and Wittes (1988):

$$1 - \Phi\left[\frac{Z_{1-\alpha} - B_{\tau} / \tau}{\sqrt{1-\tau}}\right]$$

where:

$Z_{1-\alpha}$ is the $(1-\alpha)*100\%$ percentile of the standard normal distribution (i.e., the critical value used to assess non-inferiority at the final analysis at overall one-sided significance level α).

τ is the information fraction (= proportion of patients in the first interim analysis = r/M where r is the number of patients per group in the interim analysis and M is the planned number of patients per group for the final analysis); if the interim sample sizes per group are not equal due to randomness, the harmonic mean of the sample size will be used.

$B_{\tau} = Z_{\tau} \sqrt{\tau}$ where Z_{τ} = the Farrington-Manning non-inferiority test statistic calculated on the interim observed data

Φ is the cumulative distribution function of the standard normal distribution.

Following the “promising zone” algorithm in Mehta and Pocock (2011), if the conditional power based on the planned final sample size of 110 patients is <42% or >80% at the interim stage, the study will continue as is (there will be no stoppage of the study for futility nor will there be a sample size increase). If the conditional power is between 42-80% (the promising zone), the sample size may then be re-estimated using the method described by Wang et al (2002) in order to maintain 80% conditional power without increasing the Type I error (probability of a false positive result) of the study. Specifically, the total revised sample size per group, M' required to achieve a conditional power of 80% to assess non-inferiority at the final analysis using a non-inferiority margin of 10% is found by solving the following equation for M' :

$$Z_{0.20} \sqrt{1 - \frac{r}{M'}} + Z_{\tau} \sqrt{\frac{M'}{r}} - Z_{1-\alpha} = 0$$

[figure not shown]
where $Z_{0.20}$ is the 20th percentile of the standard normal distribution (corresponding to the desired 80% conditional power) and where all other variables in this equation are defined above. M' will not exceed 166 patients for the DFU arm. This formula

assumes the interim observed effect size between treatments is the true effect size between treatments.

Results of the interim assessment will be presented by the independent statistician to a select Sponsor group. The report to the Sponsor will state if additional sample is required to achieve a conditional power of 80%, and if so, how many additional patients. If additional sample size is required, the Sponsor will make a decision to either enroll the additional patients or not enroll and accept that the primary endpoint may be under-powered. The independent statistician's report containing the results that led to the independent statistician's recommendation will be kept confidential within the select Sponsor group.

The following decision rules outline the possible outcomes of the interim analysis:

1. If the test for $CP_{ni} < 0.42$ or ≥ 0.8 , then there is no increase in the sample size and the trial will be completed on a minimum of 110 enrolled patients, as scheduled.
2. If the test for conditional power is $0.42 \leq CP_{ni} < 0.8$, then the sample size will be increased by just the right amount such that CP_{ni} is increased to 0.8, under a cap of 166 patients. The range $0.42 \leq CP_{ni} < 0.8$ is called the promising zone for non-inferiority. Specifically, if CP_{ni} is in its promising zone, this decision rule increases the sample size by the smallest of 166 patients or the number needed to boost CP_{ni} to 0.8.

CP=Conditional Power
Probability of success (statistical significance) at the end of the trial given current data trend

[figure not shown]

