9.4.2 VLU Arm

The interim analysis for the VLU arm will be performed independently of the interim analysis for the DFU arm, but it will be very similar in nature.

In the VLU arm, the analysis will be conducted when ~50% of the mITT population (30 patients) have been enrolled and completed the primary endpoint evaluation. The methods will be the same as described above. M` will not exceed 90 patients for the VLU arm.

The following decision rules outline the possible outcomes of the interim analysis:

1. If the test for CPni < 0.43 or ≥ 0.8 , then there is no increase in the sample size and the trial will be completed on a minimum of 60 enrolled patients, as scheduled.
2. If the test for conditional power is $0.43 \leq \text{CPni} < 0.8$, then the sample size will be increased by just the right amount such that CPni is increased to 0.8, under a cap of 90 patients. The range $0.43 \leq \text{CPni} < 0.8$ is called the promising zone for non-inferiority. Specifically, if CPni is in its promising zone, this decision rule increases the sample size by the smallest of 90 patients or the number needed to boost CPni to 0.8.

CP=Conditional Power
Probability of success (statistical significance) at the end of the trial given current data trend

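### The interim conditional power divides endpoint completers by planned enrolment: under the plan's own 20% loss, with nothing recovered by imputation, a computed 80% is really 72%

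*Combined protocol and SAP*

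**What the plan says.** Section 9.4.1 defines the information fraction as r/M. Here r is the per-group number in the interim analysis, and "M is the planned number of patients per group for the final analysis".

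- **Numerator.** The DFU interim is held when "50% of the mITT population (56 patients) have been enrolled and completed the primary endpoint evaluation". Section 9.4.2 triggers the VLU interim at about half "of the mITT population (30 patients) have been enrolled and completed the primary endpoint evaluation". With 1:1 randomization (Section 5.7), r is 28 and 15 per group.
- **Denominator.** Section 9.4.1 works with "conditional power based on the planned final sample size of 110 patients", and decision rule 1 shows what kind of number this is: "the trial will be completed on a minimum of 110 enrolled patients, as scheduled". For VLU the corresponding rule is "the trial will be completed on a minimum of 60 enrolled patients, as scheduled". So M is 55 and 30 per group.
- **Origin of the totals.** For DFU, Section 9.3.1 states that "this results in a sample size of 44 per group (88 total) that provides a power of 0.8 and one-sided alpha of 0.05", and then: "After allowing for an assumed 20% lost to follow up, this results in a total sample size of 110 patients". Section 9.3.2 takes the same route from 24 per group (48) to 60 for VLU.

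Section 9.6 imputes missing closure status by logistic-regression multiple imputation. It names age and gender as predictors and leaves the others to a later analysis plan.

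**The concern.** The numerator counts patients who have an outcome. The denominator counts everyone to be enrolled, including the 20% the plan expects to lose. Nothing in Section 9.4 converts one count to the other, so the information fraction is too small whenever lost patients contribute less than full information. The remaining information is then overstated, and for a favourable interim trend so is the conditional power.

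Uneven loss over time is not needed for this. At a constant 20%, 56 completers come from 56/0.8 = 70 enrolled, and 110 enrolled yield 88.

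The revised per-group size M' is affected too. It is solved on the scale of r, that is, in completers, and then used as enrolment. These two quantities decide whether the sample is increased and what number of extra patients the independent statistician gives the sponsor.

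Two wording faults in the same section do not affect the 72%. M' is defined per group but capped at 166 and 90, which Sections 1 and 3 give as total enrolment. Decision rule 2 also says the sample grows *by* the smaller number where *to* is meant.

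**Working it through.** **Inputs.** One-sided alpha 0.05 (critical value 1.645), conditional power target 0.80, margin 10 points; closure rates 75% vs 60% (DFU) and 75% vs 50% (VLU); 20% loss (all Section 9.3). r = 28 and 15; M = 55 and 30 (Section 9.4).

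**The plan's sample sizes reproduce.** The Farrington-Manning formula gives 43.1 per group for DFU, rounded up to 44 (power 0.807), and 23.1 for VLU, rounded up to 24 (power 0.814). Then 88/0.8 = 110 and 48/0.8 = 60. The enrolment totals do contain the loss allowance.

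**Conditional power.** Because B = Z√τ, the plan's formula is CP = 1 − Φ[(1.645 − Z/√τ)/√(1 − τ)].

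- DFU, as written: τ = 28/55 = 0.509. Z = 1.594 gives CP = 0.800.
- DFU, same Z, τ = 28/44 = 0.636: (1.645 − 1.999)/0.603 = −0.587, so CP = 0.721.
- VLU, as written: τ = 15/30 = 0.500. Z = 1.584 gives CP = 0.800.
- VLU, same Z, τ = 15/24 = 0.625: (1.645 − 2.003)/0.612 = −0.586, so CP = 0.721.

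The true value behind a computed 0.80 depends on the share s of enrolled patients who supply outcome information, with τ = r/(sM):

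| s | DFU | VLU |
|---|---|---|
| 1.00 | 0.800 | 0.800 |
| 0.95 | 0.783 | 0.783 |
| 0.90 | 0.764 | 0.764 |
| 0.85 | 0.744 | 0.744 |
| 0.80 | 0.721 | 0.721 |

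If the 20% are lost only after the interim, M = 28 + 0.8 × 27 = 49.6 (DFU) and 15 + 0.8 × 15 = 27 (VLU), and CP is 0.765 and 0.764. If imputation recovers half the lost information, M = 49.5 and 27, and CP is 0.764. If missingness is equal at both looks (22.4/44 and 12/24), CP stays 0.800. In the other direction, a true 0.80 at 20% loss needs a computed value of about 0.86.

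**Revised sample size.** M' solves −0.842√(1 − r/M') + Z√(M'/r) − 1.645 = 0, taking the larger root.

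- DFU example, 23/28 vs 21/28: Z = 1.540, computed CP 0.77, M' = 60.3, so 61 per group. That is 122 in total, 12 more patients. At 20% loss, 0.8 × 61 = 48.8 per group supply outcomes and CP is 0.724. Converted, 60.3/0.8 = 75.4, so 76 per group: 152 in total, 42 more, CP 0.803.
- VLU example, 13/15 vs 11/15: Z = 1.555, computed CP 0.78, M' = 31.5, so 32 per group. That is 64 in total, 4 more. At 20% loss, 25.6 per group give CP 0.726. Converted, 31.5/0.8 = 39.4, so 40 per group: 80 in total, 20 more, CP 0.805.

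**How often it matters.** Summing exact binomial probabilities over all interim tables at the design rates, with 20% loss, the increase decision changes in 11.7% of DFU trials (6.5% gain an increase, 5.2% lose one) and 9.7% of VLU trials (9.5% and 0.2%). At 10% loss the figures are 7.3% and 0%; with no loss or equal missingness, none. Increases below the cap, where M' under-enrols as in the examples, occur in 7.1% of DFU and 6.2% of VLU trials.

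**Operating characteristics.** Exact two-stage enumeration at 20% loss, without imputation, comparing the plan as written with r, M and M' put on the observed-outcome basis:

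| | As written | Consistent basis |
|---|---|---|
| Power, DFU | 0.844 | 0.837 |
| Power, VLU | 0.830 | 0.833 |
| Type I error at 50% vs 60%, DFU | 0.0469 | 0.0473 |
| Type I error at 50% vs 60%, VLU | 0.0447 | 0.0444 |
| Type I error at 65% vs 75%, DFU | 0.0518 | 0.0510 |
| Type I error at 65% vs 75%, VLU | 0.0525 | 0.0520 |

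**The case against.** The strongest reply is that the plan analyses the mITT population, which keeps every randomized patient with one application, so r need not mean completers. If 56 completers come from 70 enrolled and all 70 count, r = 35 per group and τ = 35/55 = 0.636, the same as 28/44. M' then scales to 60.3 × 35/28 = 75.4, which is the converted figure. A second reading takes the 56 as mITT patients who have reached the evaluation time, observed or not; missingness is then similar at both looks and 0.80 stands.

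Neither reading is what the text says. The trigger is completion of the endpoint evaluation, and Z is calculated on observed interim data. Counting 70 patients conflicts with the plan's own label of 56 as half the mITT population. It also fits the 0.42 cutoff less well: a promising-zone lower bound computed from 56, 110 and the cap of 166 is 0.420, against 0.411 on the 0.636 fraction. This is supportive, not proof, and it does not separate the plan's text from the second reading.

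Three points stand. First, 72% is the worst case considered: it needs the full 20% loss and no information from imputation, whose predictors are not yet all named. Second, overall power and type I error barely change, and DFU power falls slightly under the fix. Third, the sponsor may decline an increase in any case.

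**Conclusion.** The concern holds as the plan is written. Section 9.4 divides completers by enrolment, and a computed conditional power of 0.80 corresponds to between 0.72 and 0.80 in both arms. The lower end assumes the plan's 20% loss with no recovery by imputation; the upper end assumes no loss, full recovery, or equal missingness at both looks. At 20% loss, the number of extra patients reported can be too small by 30 in the DFU example (12 instead of 42) and by 16 in the VLU example (4 instead of 20).

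The damage is to the decision and the number given to the sponsor, not to the validity of the final test: type I error moves by at most 0.1 percentage point. This should be corrected, at modest priority.

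**What to change.** In Sections 9.4.1 and 9.4.2, before any unblinded interim data are seen:

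1. Define r, M and M' as patients per group with an observed primary outcome. Set M to 44 (DFU) and 24 (VLU), or to planned enrolment times the completion rate observed at the interim; specify in advance which.
2. Convert M' to enrolment by dividing by that same completion rate (0.8 if the planning value is used).
3. State how patients with imputed outcomes count in r and M.
4. State the caps as total enrolment, 166 (83 per group) and 90 (45 per group), and have decision rule 2 increase the sample *to* the smaller number.

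The lower bounds of 0.42 and 0.43 can stay. On the 44/24 basis, with the caps scaled to 83 × 0.8 = 66.4 and 45 × 0.8 = 36 per group, the smallest bound that protects type I error is about 0.41 in both arms.

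The cost is wording, plus less favourable reported conditional power. At 20% loss and the design rates, the share of trials increased goes from 15.9% to 17.2% (DFU) and from 12.2% to 21.4% (VLU). Mean enrolment goes from 117.3 to 116.7 and from 63.2 to 63.9. Results with a computed conditional power of about 0.42 to 0.53 (DFU) or 0.43 to 0.54 (VLU) would lose an increase. DFU power falls by 0.7 point and VLU power rises by 0.3 point.
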